2.2 Hormone Therapy

Since testosterone is the main growth and survival factor for prostate cancer most patients will respond initially to ablation of gonadal androgen production through surgical (bilateral orchiectomy) or medical (luteinizing hormone-releasing hormone (LHRH) agonist or antagonist therapy [39]) approaches[16]. Unfortunately eventually all patients will develop progressive disease despite continued androgen suppression, with a median time to progression of 14 to 30 months[17]. There are many mechanisms responsible for the development of resistance to androgen deprivation. They include amplification of androgen receptors, increased sensitivity of androgen receptors, mutations of androgen receptors that allow activation by non-androgenic ligands and activation of alternative survival pathways[18]. Recent data suggests that early application of docetaxel chemotherapy in addition to androgen suppression results in significant survival extension in patients with metastatic hormone sensitive prostate cancer, but this benefit appears to be particularly robust in patients with extensive metastatic disease and data for patients with oligometastatic disease (our study population) is not compelling[19].

Unfortunately once resistance to hormone therapy occurs, prognosis is dismal. This so-called castration resistant prostate cancer (CRPC) is characterized by virulent biologic and clinical behavior with median survival of 18-35 months[20]. Multiple life –extending agents have been approved in the last 10 years for the treatment of CRPC including immunotherapy (Sipuleucel-T), second generation androgen-pathway inhibitors (abiraterone, enzalutamide), chemotherapy (docetaxel, cabazitaxel) and radioactive isotope Radium Ra 223 dichloride[20]; however no significant therapeutic progress has been made in patients with hormone sensitive disease outside of subset with extensive metastases[19].

2.3 Radium Ra 223 Dichloride

Radium Ra 223 dichloride is an α emitting, bone seeking calcium-mimetic that selectively targets and binds to increased areas of bone turnover in bone metastases. The drug is administered by intravenous injection at four week intervals for a total of six injections.

2.3.1 Clinical experience

The ALSYMPCA trial was a randomized, double blind, Phase 3 study that compared six injections of radium Ra 223 dichloride against placebo in men with CRPC and bony metastases who had received, were not eligible to receive, or had declined docetaxel chemotherapy[21]. Median overall survival was longer with

radium Ra 223 dichloride than placebo (14.9 v 11.3 months; hazard ratio 0.70, 0.58 to 0.83; $P < 0.001$). Subsequent subgroup analysis showed a survival benefit with radium Ra 223 dichloride, irrespective of previous docetaxel use. In addition, a significant improvement in median time to first symptomatic skeletal event was seen for radium Ra 223 dichloride versus placebo (15.6 v 9.8 months; hazard ratio 0.66, 0.52 to 0.83; $P < 0.001$). Radium Ra 223 dichloride was well tolerated and associated with fewer adverse events than placebo. Although the difference was not significant, a slightly higher rate of diarrhea (25% v 15%) was seen with radium than with placebo. Other known side effects include nausea, vomiting, peripheral edema, and hematologic abnormalities (anemia, leukopenia, thrombocytopenia, neutropenia). It is notable that hematologic toxicities of Radium 223 were modest even in this population of patients with very advanced, and heavily pretreated disease. A meaningful improvement in quality of life was also noted for radium compared with placebo. The American Urological Association (AUA) guideline recommends radium Ra 223 dichloride for use in patients with CRPC with bony metastases, no known visceral metastases, and good performance status, irrespective of previous docetaxel use. Radium Ra 223 dichloride has always been used in conjunction with ongoing ADT therefore safety data for that combination is established.

2.4 Stereotactic radiation therapy

Stereotactic body radiation treatment (SBRT) for oligometastatic disease has emerged as a treatment modality to improve local control of metastases and delay need for toxic systemic treatment. There are numerous studies utilizing SBRT for oligometastatic patients with various histologies. For prostate in particular there have been a few recent papers documenting safety and efficacy of treating oligometastatic prostate cancer patients.

One such study from Philadelphia looked at the benefit of SBRT in patients heavily treated for metastatic prostate cancer[22]. 24 patients were treated and there was improved median survival (>3yrs vs. 11 months) for patients with ≤ 4 oligometastases. The radiation dose for SBRT was 24 Gy (18-50Gy) in 3 to 5 fractions (8Gy x 3). Most sites were bone and lymph nodes and toxicity was only reported in 2 patients, one with grade 1 diarrhea and one with Grade 2 pelvic pain[22].

Another study from Belgium looked at benefit of SBRT for newly diagnosed oligometastatic patients[23]. Their dose was 50 Gy in 10 fractions (40-50Gy in 8-10 fractions, dose sculpted to respect normal tissue tolerances) for newly metastatic patients presenting with three synchronous oligometastases (bone and or lymph nodes). Berkovic *et al.*[23] demonstrated that SBRT was able to defer palliative androgen deprivation therapy for a median of 38 months and was safe with no Grade 3 toxicity observed.

Of note there are two ongoing multi-institutional trials using androgen deprivation and SBRT radiation for the bulk of the metastatic prostate cancer already but none thus far combining with xofigo to eradicate micrometastatic disease NRG BR001 A Phase 1 Study of Stereotactic Body Radiotherapy (SBRT) for the Treatment of Multiple Metastases and STOMP surveillance or metastasis-directed therapy for oligometastatic prostate cancer recurrence[24]. In the multi-institutional NRG BR001 Phase 1 study, oligometastatic breast, lung, or prostate patients are eligible to receive radiation to ≤ 4 metastatic sites. For prostate in particular the continuation of androgen deprivation is allowed. The radiation doses are in the range of 10-15Gy per fraction for 3 to 5 days as compared to palliative radiation given in doses of 3Gy per fractions for 10 days. The Phase 1 portion of this trial for bone has already met accrual and results are pending.

In the STOMP trial, prostate patients with oligometastatic recurrence of prostate cancer are eligible to receive SBRT[24]. The trial is limited to SBRT alone without concurrent systemic treatment. It is a randomized Phase 2 study to see if there is benefit of SBRT versus active surveillance of patients with

oligometastatic prostate cancer. The hypothesis is that patients treated with SBRT will have a longer ADT free survival and longer time to initiation of long term androgen deprivation use. The trial delineates radiation dose guidelines for lymph node and bone metastases. The dose is 10Gy x 3 fractions building from prior studies of this same groups utilizing this SBRT radiation dose with concomitant androgen deprivation therapy[24]. Toxicities from this SBRT regimen were mild and of 50 patients treated, only 10 patients had either Grade 1 or 2 toxicities[24]. The 50 patients had 70 metastatic lesions treated and local control of 100%; lesions included mostly bone and lymph nodes with only 2% visceral metastases; from 2005-2012 the dose was 50Gy in 10 fractions and from 2012-2014 the dose was 30Gy in 3 fractions. Our study is limiting to lymph node and bone metastases using similar radiation dose guidelines of both the STOMP trial and the NRG BR001 trial. The STOMP trial has now been published and demonstrated that SBRT to multiple metastatic sites (three or less) is safe and does delay metastatic progression and thus initiation of androgen deprivation therapy (ADT) (Ost et al 2018)[14]. The median ADT-free survival was 13 months for the observation/active surveillance group and 21 months for the metastasis-directed therapy group (either surgery, radiation or a combination)[14].

A recent National Cancer Database (NCDB) analysis of metastatic prostate cancer patients demonstrated that patients who received radiation to prostate primary had improved overall survival on both univariate and multivariate analysis[25]. On univariate analysis 5 year OS improved from 25% to 49% and 8yr OS estimates improved from 13% to 33%). Radiation dose over 65Gy was associated with improved overall survival consistent with reports of men with localized prostate cancer. Cho *et al.* [26]also demonstrated improved overall survival in metastatic prostate patients who received radiation to prostate primary in addition to ADT (3 yr OS increased from 43% to 69%) [26]. A large phase III trial of over 2000 patients, STAMPEDE, also showed improved survival with definitive radiation to the prostate primary in the subset of patients with limited metastatic disease (low burden metastatic burden) [27]. 3 year OS in this limited metastatic disease subset of STAMPEDE increased from 73% to 81% with HR of 0.68 (p value of .0098)[27]. In the STAMPEDE trial limited metastatic disease was defined as <4 bone metastases and no visceral metastases (i.e. lung, liver metastases) [27]. Lymph nodes were not included in the metastatic definition (i.e. visceral disease always recorded as nonnodal and in STAMPEDE over 60% had lymph nodes N+ disease) [27]. There has also been a recent abstract of adding definitive prostate radiation (74Gy to prostate, 60Gy to lymph nodes) concurrent with Ra-223 but no SBRT (ADRRAD trial); recent abstract shows this regimen to be safe and early promising results on whole body MRI [28]. Also in our predecessor trial IRB# 05190, approximately 50% of patients on the trial had definitive prostate radiation (+/- close proximity lymph nodes) [10, 29]. Due to the recent literature, recent change in NCCN and Via Oncology guidelines and that our predecessor trial allowed definitive prostate radiation we are now allowing definitive radiation to the prostate prior to cycle 1 of this trial.

Other earlier papers also analyzing large databases have demonstrated benefit of radical prostatectomy in men with metastatic prostate cancer[30-33]. We have been allowing radical prostatectomy prior to cycle 1 of this trial as well and will continue to allow patient choice of treatment for untreated prostate primary similar to our predecessor trial IRB #05190 [10, 29].

2.5 Bone Health Agents

To optimize treatment with androgen deprivation therapy, Ra-223 and SBRT, we must minimize risk of adverse events. In particular, non-pathologic fractures are an area of concern. Patients on this study are required to take bone health agents (BHAs) including bisphosphonates or RANKL inhibitors, from the start of protocol therapy (approximately) until the participant's testosterone levels are within the normal range or at the discretion of the PI.

The present study is a phase II trial on the use of Ra-223 with ADT and SBRT for metastatic castrate sensitive prostate cancer (mCSPC) patients. Each treatment agent on this study independently increases fracture risk. Ra-223 alone was shown to increase fracture risk in the REASURE study, a prospective trial on fracture risk in patients receiving Ra-223 monotherapy. For the Ra-223 cohort (n=36), 74 new fractures were identified in 20 patients (56%) at a median follow-up of 16.3 months, while for the reference cohort (n=36), 16 new fractures were identified in 12 patients (33%) at a median follow-up of 24 months [34]. Radiation therapy is also associated with a high incidence of fractures. A meta-analysis of 21 studies and 3929 patients with gynecologic cancers who received external beam radiation therapy found that pelvic insufficiency fractures occurred in 14% of patients, with 73.6% of fractures developing in the sacral bone or joint. The median time to fracture was 7.1 to 19 months post-radiation therapy [35]. The effect of ADT on fracture risk was described in a nationwide cohort study (n=144,670) in Korea, which showed that in patients with prostate cancer, ADT significantly increases the risk of newly developed fractures (HR, 1.815; 95% CI, 1.703–1.935; $p < 0.0001$) and osteoporosis (HR, 1.381; 95% CI, 1.305–1.461; $p < 0.0001$) compared to those not receiving ADT, and this is positively correlated with the duration of ADT [36].

Patients receiving androgen deprivation therapy (ADT) and Radium-223 (Ra-223) in combination face a significantly increased risk of non-pathological fractures. The phase 3 ERA 223 study on metastatic castrate resistant prostate cancer (mCRPC) patients was unblinded prematurely after an unplanned ad-hoc analysis revealed significantly increased fracture rates with the addition of Ra-223 to treatment with abiraterone acetate and prednisone or prednisolone. While fractures of any grade occurred in 11% of patients receiving a placebo instead of Ra-223, this increased to 29% of patients for the group receiving Ra-223 [37]. 78% of all fractures occurred at uninvolved sites, not metastatic sites.

BHAs have been shown to reduce the occurrence of fractures in this setting. On the ERA 223 study, the use of bone health agents (BHAs) was only allowed for patients who were on BHAs at baseline, which was around 40% of the study population. No patients were permitted to initiate BHA use while on study. They reported that in both the Ra-223 and placebo groups, patients on BHAs from baseline were associated with a lower fracture rate. For the Ra-223 group, fractures occurred in 15% of patients using BHAs, compared to 37% of patients not using BHAs. For the placebo group, fractures occurred in 7% of patients using BHAs, compared to 15% of patients not using BHAs [38].

After the ERA223 trial reported the increased risk of fractures with the addition of Ra-223, the EORTC1333/PEACE III trial was amended to mandate that all patients must start using a BHA. This trial compared enzalutamide and Ra-223 to enzalutamide alone for mCRPC patients, and reported that when Ra-223 is combined with enzalutamide treatment, the risk of fracture significantly increases from 13% to 33%. They found that when BHAs are used a minimum of 6 weeks before the first administration of Ra-223, this risk is almost abolished [39]. The results of these studies necessitate BHA use in our present study, as Ra-223, ADT and SBRT are used in a combined treatment regimen. The need for BHA use is clearly demonstrated for mCRPC patients treated with ADT and Ra-223. BHAs like bisphosphonates and RANKL inhibitors are also indicated for use in mCSPC patients on ADT to prevent treatment-induced bone loss and resulting fractures at a dosage of 60 mg denosumab every 6 months or 5 mg zoledronic acid once per year, respectively [40]. Patients on this study will be required to take bisphosphonates or RANKL inhibitors to reduce the risk of fracture associated with Ra-223, ADT and SBRT.

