7.4 Relugolix

The expected toxicities for relugolix are as follows (* signifies $\geq 20\%$; no asterisk signifies 3-20%, and † signifies $<3\%$):

Vascular	Hot flush*, stroke†
Musculoskeletal and Connective Tissue	Musculoskeletal pain*, fracture†
General	Fatigue*
Gastrointestinal	Diarrhea, constipation, abdominal pain†

Investigations (excluding hematological labs)	Increased glucose*, increased triglycerides*, increased alanine aminotransferase*, increased aspartate aminotransferase, increased transaminases†
Cardiac	Myocardial infarction†, arrhythmia†, atrioventricular block†, cardiac failure†
Blood and lymphatic	Decreased hemoglobin*, hemorrhage†
Renal	Urinary tract infection†, acute kidney injury†
Respiratory	Pneumonia†

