7.6 Radium Ra 223 dichloride

7.6.1 Radiation exposure:

In general, administration of radioactive drugs involves a potential risk for third parties because of radiation from the participant and possible contamination by spilling urine or feces. When radium Ra 223 dichloride has been injected intravenously into a participant, the risk for external radiation exposure to third parties is extremely low, because of the short range of the α particles ($<100\ \mu\text{m}$) and the low portion of β and γ radiation. For these reasons, the product can be administered on an out-patient basis.

To minimize the risk of contamination, participants and his caregivers will receive oral and written instructions regarding hygiene precautions to abide by after receiving radium Ra 223 dichloride.

7.6.2 Side-effects:

The expected toxicities for radium Ra 223 dichloride are as follows (no asterisk signifies $\geq 10\%$; * signifies 1-10%, and † signifies $<1\%$):

Blood and lymphatic (including hematological labs)	Anemia, lymphocytopenia, leukopenia, thrombocytopenia, neutropenia
Gastrointestinal	Nausea, diarrhea, vomiting
General Disorders and Administration Site	Peripheral edema, injection site reaction*
Metabolism and Nutrition	Dehydration*
Neoplasms benign, malignant and unspecified (incl cysts and polyps)	Treatment related secondary malignancy†
Renal and urinary	Renal failure and impairment*

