13.4 Stopping Rules for Excessive Toxicity

The stopping rules for safety/toxicity will be assessed for each patient after the first 2 cycles of radium dichloride 223. The expected rate of unacceptable toxicity should not be $\geq 33\%$.

A patient will be deemed to have experienced an Unacceptable Toxicity (UT) if any of the following occur during the **first 2 cycles of radium Ra 223 dichloride (Cycles 2 and 3)** and are attributed as possibly, probably, or definitely related to protocol therapy:

- **Hematological**
 - Any \geq Grade 3 hematological toxicity that delays the next planned dose of radium Ra 223 dichloride by > 28 days

○ *Non-hematological*

- Any >Grade 2 fracture
- Any \geq Grade 3 non-hematological toxicity that does not resolve to \leq Grade 2 with adequate supportive care and delays the next planned dose of radium Ra 223 dichloride by > 28 days
- Any recurrent \geq Grade 3 toxicity

The following table will be consulted as relevant toxicities defined above are encountered.

When a stopping rule is triggered, the study PMT will review and assess the safety of the trial and submit a report to the COH DSMC. The COH DSMC will review for approval any decision to continue accrual, amend the protocol, or permanently suspend accrual to the trial.

# of patients treated that determines early stopping	# of patients with unacceptable toxicity	Given the following toxicity rates, cumulative probability of early stopping:		
		10%	25%	35%
≤ 6	2	0.11	0.47	0.68
≤ 10	3	0.14	0.56	0.80
≤ 12	4	0.14	0.58	0.81
≤ 15	5	0.14	0.59	0.83
≤ 18	6	0.14	0.60	0.85
≤ 21	7	0.14	0.61	0.86
< 24	8	0.14	0.61	0.86

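### The toxicity stopping rule counts a fracture above Grade 2 only if it is judged related, although Section 2.5 says every study agent raises fracture risk and most of the Section 7 toxicity lists omit fracture

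*Combined protocol and SAP*

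**What the plan says.** **Risk statement.** Section 2.5 says of ADT, SBRT and radium: "Each treatment agent on this study independently increases fracture risk". It cites a phase 3 trial of radium with abiraterone in castration-resistant disease. Fractures of any grade occurred in 11% on placebo and "this increased to 29% of patients for the group receiving Ra-223"; among radium patients using bone health agents the figure was 15%. In that trial "78% of all fractures occurred at uninvolved sites, not metastatic sites". It also cites a radium cohort with fractures in 56% at a median of 16.3 months, against 33% in a reference cohort at 24 months.

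**Toxicity lists.** Section 7.6.2 opens with "The expected toxicities for radium Ra 223 dichloride are as follows" and has neither a fracture entry nor a musculoskeletal row. The leuprolide (7.1), goserelin (7.2) and degarelix (7.3) lists do not name fracture either, though goserelin's includes loss of bone mineral density. Fracture is named for relugolix in 7.4 ("Musculoskeletal pain*, fracture", marked as under 3%). It is also named for SBRT in 7.5, under spine metastases (compression fracture of the treated vertebra) and bone metastases (1-10%). Section 9.1.5, on human toxicity of radium, refers to Section 7.4, which is relugolix.

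**Stopping rule.** Section 13.4 lists "Any >Grade 2 fracture" as an unacceptable toxicity, with no dose-delay condition. All unacceptable toxicities must fall in the first two radium cycles and be "attributed as possibly, probably, or definitely related to protocol therapy". Under Section 8.1 the PI or a designee makes the attribution.

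**The concern.** The evidence in Section 2.5 that radium raises fracture risk is comparative: it rests on differences between groups. This trial has no comparator, 24 evaluable patients, three treatments each said to raise the risk, and men on ADT who have a background risk of their own. Nobody can tell from a single fracture whether treatment caused it, so attribution adds a subjective filter without adding information.

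The lists make the judgement less consistent. A fracture away from an SBRT site, in a man on leuprolide plus radium, matches no listed toxicity. By the cited trial's figure, fractures at uninvolved sites are the common kind. An assessor working from Section 7 and one working from Section 2.5 could reach different answers.

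At stake is the sensitivity of the stopping rule. The probabilities printed in Section 13.4 describe the rate of counted events and make no allowance for events judged unrelated.

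**Working it through.** **1. Reproduce the plan's table.** Inputs are the Section 13.4 boundaries: 2 events by 6 patients, 3 by 10, 4 by 12, 5 by 15, 6 by 18, 7 by 21, 8 by 24. An exact binomial recursion over patients 1 to 24, absorbing at these boundaries, gives:

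| True rate | Printed, last row | Recomputed (last row ends at 24) | Recomputed (ends at 23) |
|---|---|---|---|
| 10% | 0.14 | 0.138 | 0.138 |
| 25% | 0.61 | 0.623 | 0.618 |
| 35% | 0.86 | 0.873 | 0.866 |

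The table is sound. All 21 cells agree within 2 percentage points.

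**2. How many fractures could fall in the window?** The window is two 28-day cycles, 56 days or 56/30.4375 = 1.84 months. The documents give no rate for it. Assume a constant hazard and that the cited any-grade proportions accrued over 12 to 24 months (both assumptions). With cited proportion F over T months, hazard h = -ln(1 - F)/T, and the proportion in the window is x = 1 - exp(-1.84 h).

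| F | T = 12 months | T = 24 months |
|---|---|---|
| 15% (radium with bone health agents) | 2.5% | 1.2% |
| 29% (radium, all) | 5.1% | 2.6% |

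So x is about 1-5%. The rule needs a fracture above Grade 2, so any-grade proportions lean high.

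**3. Effect of leaving some out.** Let f be the share of these fractures judged at least possibly related. The documents give no value. I use 22% to 50% as a pessimistic range (assumption). Counted rate = true rate - x(1 - f).

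| True rate | x | f | Counted rate | P(stop by 24) |
|---|---|---|---|---|
| 35% | none lost | 1 | 35.0% | 0.87 |
| 35% | 1.2% | 0.50 | 34.4% | 0.86 |
| 35% | 5.1% | 0.22 | 31.0% | 0.79 |
| 25% | none lost | 1 | 25.0% | 0.62 |
| 25% | 1.2% | 0.50 | 24.4% | 0.60 |
| 25% | 5.1% | 0.22 | 21.0% | 0.49 |

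**4. Stretch case.** The 56% cohort over 16.3 months gives x of about 8.9%, any grade. With the same f, P(stop) would be about 0.72-0.78 at 35% and 0.39-0.47 at 25%. I treat this as an outer bound.

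**5. Cost of counting every fracture.** If unrelated traumatic fractures add 1 to 2 points to a true 10% rate, P(stop) rises from 0.138 at 10% to 0.164 at 11% and 0.192 at 12%.

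**The case against.** The case for leaving the rule alone is substantial.

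- **The bar is low.** The condition refers to protocol therapy as a whole, and Section 8.1 defines a possible relation as one where the event may be related even if another cause may also exist. Given Section 2.5, calling a fracture unrelated would be hard to defend. If every fracture is called possible, nothing is lost. This stands, and it is why the point is an opening only.
- **Section 7 does not govern attribution.** A reader might infer that a fracture missing from the radium list must be called unrelated. The documents do not say so. Section 7 lists expected toxicities, Section 8.1 defines attribution separately, and an unlisted event could instead be handled as unexpected, which invites more scrutiny.
- **The 78% figure is not an attribution rate.** A reader might take the remaining 22% at involved sites as the share that would be judged related. Site is not relatedness, and Section 2.5 cites uninvolved-site fractures as evidence of treatment harm. The 22% above is only a pessimistic assumption.
- **The effect is small.** A reader might suppose that fractures make up much of the unacceptable toxicity. If they were half of a 35% rate, 17.5% of men would fracture above Grade 2 within 56 days. The cited any-grade rates imply about 1-5%, or about 9% from the highest cohort.
- **Other safeguards exist.** Adverse events are recorded whether or not related, serious ones are reported, and a DSMC with no direct link to the study reviews toxicity.

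What survives is that the protocol gives two answers on which agents carry fracture risk, and that its stopping count passes through a judgement a single-arm trial cannot inform.

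**Conclusion.** The point holds as a cheap improvement. Sections 2.5 and 7 disagree and should be reconciled, and the Section 9.1.5 reference is wrong; neither conclusion needs any assumption. The attribution condition could remove some fractures from the stopping count. On the stated assumptions (constant hazard over 12-24 months, cited any-grade rates of 15-29%, 22-50% attributed) the loss is 1 to 8 percentage points of stopping probability at a true 35% rate and about 2 to 13 points at 25%. If all fractures are judged possible, the loss is zero.

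The documents do not support saying that fractures will be systematically excluded, or that the trial would therefore report the combination as tolerable when it is not. Section 2.5 calls non-pathologic fractures an area of concern; it does not rank them above other harms.

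**What to change.** - **Section 13.4:** count any fracture above Grade 2 in Cycles 2-3 regardless of attribution, and keep the attribution condition for the other toxicities.
- **Section 7:** reconcile the radium, leuprolide, goserelin and degarelix lists with Section 2.5, so that expectedness and attribution draw on the same risk information.
- **Section 9.1.5:** point to Section 7.6. The same renumbering slip appears in 9.2.3.5 (degarelix, sent to 7.2) and 9.3.2.1 (SBRT, sent to 7.3).

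The cost is a few words. An occasional traumatic fracture would count, raising the stopping probability from 0.14 to 0.16-0.19 if it adds 1-2 points to a 10% rate. Under Section 13.4 a trigger leads to review by the Protocol Management Team and the DSMC, and does not end the trial automatically. The boundaries and the printed table need no change.
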